5.5.3 Labelling

Labels will be prepared in accordance with Good Manufacturing Practice (GMP) and local regulatory guidelines. The labels will fulfil GMP Annex 13 requirements for labelling. Label text will be translated into local language.

5.5.4 Storage

All study medications should be kept in a secure place under appropriate storage conditions. The study medication label on the study supplies and the IB specifies the appropriate storage.

5.6 **Concomitant and post-randomisation treatment(s)**

Recording of concomitant medications will be made at each visit. Medications of special interest including study medication, other antiplatelet medications, proton-pump inhibitors (PPIs) and statins will be captured in detail. Other medications of interest will be captured by class and ongoing use. Complete concomitant medication information will be recorded perievent for any SAE or permanent discontinuation of study medication due to an AE.

5.6.1 Oral antiplatelet therapies

Concomitant ASA at start of study: Patients requiring dual antiplatelet therapy (e.g. aspirin plus clopidogrel, aspirin plus prasugrel, or aspirin plus dipyridamole) will be excluded at study entry, as the purpose of this study is to primarily test the benefits of mono-antiplatelet therapy.

• Low Dose ASA (defined as ≤ 150 mg od) added during the study: patients who develop an indication for aspirin therapy after randomisation will follow the guidelines below. If concomitant ASA is needed during the study, it will be sourced locally.

If the patient develops ACS (per AHA/ESC definition) or undergoes Percutaneous Coronary Intervention (PCI) without having ACS:

- The patient should receive a loading dose of ASA (determined and recorded by the treating investigator) and then daily low-dose ASA thereafter (defined as \leq 150 mg od) consistent with current practice guidelines.
- The patient should continue to take study medication.
- If a loading dose of ticagrelor or clopidogrel is desired, the investigator should utilise the study medications, giving both of the double-dummy medications, eg, to load for an interventional procedure (PCI), take (1) additional ticagrelor/placebo tablet and (4 to 8) additional clopidogrel/placebo tablets; the investigator will determine how many (4 to 8) of the clopidogrel tablets to be taken depending on the desire to load with 300mg or 600 mg of clopidogrel.

If the patient requires peripheral percutaneous revascularization:

- Following Bare Metal Stent implantation, concomitant low dose ASA (defined as $\leq 150 \text{ mg od}$) is recommended for up to 1 month duration per current guidelines.

 Following Drug Eluting Stent implantation, concomitant low dose ASA (defined as ≤ 150 mg od) is recommended for a minimum of 1 month duration per current guidelines.

If the patient suffers a stroke:

- The patient will stop study medication immediately following the stroke event.
- The investigator will treat the patient according to current practice guidelines.
 Once it is considered safe and the investigator is willing, the patient will resume blinded monotherapy study medication.

• Use of High Dose ASA (> 150 mg)

The concomitant use of aspirin in any dose > 150 mg during the study is permitted only as a single, loading dose, regardless of circumstances (ie, prior MI, ACS, stroke, stent placement of any kind, etc). Long-term maintenance doses of aspirin > 150 mg are not permitted.

Other ADP receptor blockers (eg, prasugrel, ticlopidine):

Planned concomitant treatment with any of other ADP receptor blockers is not allowed in the study. If open-label treatment with any of these drugs is considered essential during the study, blinded study medication must be discontinued but may be resumed when open-label treatment with the ADP receptor blocker drug is stopped.

Dipyridamole

Planned concomitant chronic treatment with dipyridamole is not allowed in the study. If open-label treatment with dipyridamole, whether or not in combination with aspirin, is considered essential during the study, blinded study medication must be discontinued but should be resumed when open-label treatment with dipyridamole is stopped.

5.6.2 Approved PDE3 inhibitors for claudication (eg, cilostazol)

Planned concomitant treatment with any approved PDE3 inhibitor (ie, cilostazol) is permitted during the study.

5.6.3 Non-steroidal anti-inflammatory drugs (NSAIDs)

Clinical experience with NSAIDS in combination with ticagrelor is limited at this time. Treatment with NSAIDS is allowed during the study at the investigator's discretion. However, chronic daily dosing with non-selective NSAIDS (eg, patients with rheumatoid arthritis) may increase the potential for gastrointestinal bleeding, so either alternative therapy or concomitant acid suppression therapy is recommended. Treatment with selective cycloxygenase-2 inhibitors is permitted, although use is cautioned (Antman 2007). When pain management is needed, acetaminophen is preferred. Chronic therapy with aspirin for pain is prohibited.

5.6.4 Parenteral anticoagulants

Short-term treatment (ie, up to 7 days) with approved parenteral anticoagulants (eg. unfractionated heparin (UFH), low-molecular-weight heparin (LMWH), bivalirudin, fondaparinux) is allowed. However, long-term treatment with LMWH or fondaparinux in outpatients (at venous thrombosis treatment or atrial fibrillation doses) in combination with study medication is not allowed. Concomitant treatment with venous thrombosis prophylaxis doses is allowed. If long-term treatment with parenteral anticoagulant drugs at therapeutic doses is considered essential during the study, study medication must be discontinued, but should be resumed if parenteral anticoagulant therapy is stopped.

5.6.5 GPIIb/IIIa receptor antagonists

Short-term treatment (ie, up to 7 days) with GPIIb/IIIa receptor antagonists is allowed during the study.

5.6.6 Oral anticoagulants

Concomitant treatment with oral anticoagulant drugs (ie, vitamin K antagonists, direct thrombin inhibitors, factor X inhibitors) is not permitted during the study. If treatment with oral anticoagulant drugs is considered essential during the study, study medication must be discontinued, but should be resumed if oral anticoagulant therapy is stopped. Patients should continue to be followed as defined in section 5.8.1.

5.6.7 Fibrinolytics

Clinical experience with fibrinolytics in combination with ticagrelor is limited at this time and caution should be used. If a patient is to be treated with fibrinolytic therapy, study medication should be stopped and restarted no earlier than 24 hours after completion of fibrinolytic therapy and when the risk of bleeding is deemed low in the judgment of the investigator.

5.6.8 Digoxin and other p-glycoprotein interactions

Ticagrelor modestly increases digoxin levels. Therefore digoxin levels should be monitored closely following initiation of study medication and with any change in study medication. Other p-glycoprotein substrates may be expected to have similar changes in pharmacokinetics. For additional details reference the IB.

5.6.9 CYP450 interactions

5.6.9.1 CYP3A inhibitors

Strong inhibitors of CYP3A enzyme (eg, ketoconazole, itraconazole, voriconazole, telithromycin, clarithromycin [but not erythromycin or azithromycin], nefazadone, ritonavir, saquinavir, nelfinavir, indinavir, atazanavir, or over 1 litre daily of grapefruit juice) should not be co-administered with ticagrelor, as plasma levels of ticagrelor would be substantially increased.

5.6.9.2 CYP3A substrates or inducers

Concomitant therapy with simvastatin or lovastatin at doses higher than 40 mg daily is not permitted since administration with ticagrelor will result in higher serum concentrations and may put patients receiving more than 40 mg per day of simvastatin or lovastatin at increased risk of statin-related adverse effects. There are no restrictions to other statin therapies (ie, doses of simvastatin or lovastatin \leq 40 mg daily or any dose of any other statin is permitted). Investigators are advised to check lipid levels and adjust statin dosages per local practice and appropriate guidelines.Standard monitoring of patients for possible statin-associated myopathy should be conducted.

Co-administration of ticagrelor with strong inducers of CYP3A also should be avoided (eg, rifampin/rifampicin, rifabutin, phenytoin, carbamazepine, phenobarbital).

Discontinuation of study medication is up to the judgment of the investigator. If continued antiplatelet medication is judged necessary, there may be a need for extra caution regarding bleeding tendency.

5.6.9.3 CYP2C19 inhibitors

Ticagrelor is not metabolised via CYP2C19. In contrast, clopidogrel is a prodrug that needs to be metabolised to its active metabolite in part by CYP2C19. Concomitant use of drugs that inhibit the activity of this enzyme results in reduced plasma concentrations of the active metabolite of clopidogrel and a reduction in platelet inhibition. Thus, for patients who are being treated with study medication (ie, potentially randomised to clopidogrel treatment), the use of omeprazole or esomeprazole is prohibited, however the use of other proton pump inhibitors (PPIs) is allowed. Avoid concomitant use of other strong or moderate CYP2C19 inhibitors during the study. The concomitant use of PPIs will be recorded in the electronic case report form (eCRF).

5.6.10 Surgery

It is recommended that cardiac surgery and major non-cardiac surgery that in the opinion of the Investigator poses a risk for clinically major bleeding not be performed until at least 5 days after stopping study medication to avoid excessive bleeding. However, one should follow local treatment guidelines and protocols. There is a trade-off between stopping study medication too early and risking thrombotic events versus continuing treatment too close to surgery and risking haemorrhage. Thus it is also recommended that study medication not be discontinued for significantly longer than 5 days so as to minimise the risk of thrombotic complications while off study medication.

Other medication, which is considered necessary for the patient's safety and well being, may be given at the discretion of the investigator.

After surgery, study medications should be restarted when the risk of bleeding is deemed low in the judgment of the investigator.

5.6.11 Other surgery and invasive non-cardiovascular procedures

For other surgery or other invasive procedures, study medication may be continued or interrupted temporarily at the discretion of the investigator. As with all other surgeries, investigators should collect and record all peri-procedural bleeding events.

After the surgery or procedure, study medications should be restarted (if interrupted) as soon as possible. Regarding prevention of postoperative thrombosis, see Section 5.6.4.

Other medication, which is considered necessary for the patient's safety and well being, may be given at the discretion of the investigator.

5.7 Treatment compliance

The administration of all medication (including study medications) should be documented in the patient's medical record and recorded in the eCRF where appropriate.

Patients will be asked to return all unused study medications and empty packages to the clinic at each visit. The patient's compliance will be assessed by the investigator or designee and recorded in the eCRF. A pill count should be done at a patient level and recorded in the eCRF and a dispensing log by the study centre personnel.

5.7.1 Accountability

The study medication provided for this study will be used only as directed in the study protocol.

The study personnel will account for all study medication dispensed and returned. This record keeping consists of a dispensing log including the identification of the person to whom the drug is dispensed, the quantity dispensed, the date of dispensing, the quantity returned and the date returned.

Patients will be asked to return all unused study medication to the investigational centre at each visit. The investigator or delegate will enter the amount of returned tablets on the eCRF and make an assessment regarding patient treatment compliance. In addition, the investigator or delegate will enter the amount of returned tablets on the dispensing log or similar log according to local practice at centre. Any patient found to be noncompliant will be counselled on the importance of taking their study medication as prescribed.

Any study medication deliberately or accidentally destroyed must be recorded. Any discrepancy between dispensed and returned study medication should be explained.

The investigator will retain the returned medication until the study monitor or delegate collects it, along with any medication not dispensed. The monitor is responsible for confirming the investigator or delegate has recorded the quantities of returned and unused tablets at a patient level before medication is returned to the sponsor and/or destroyed. Following drug accountability, the study monitor or delegate will advise on the appropriate

method for destruction of unused study medication. Destruction of study medication must only be conducted by an authorised centre.

5.8 Discontinuation of study medication

Patients should be discontinued from study medication in the following situations:

5.8.1 Temporary discontinuation from study medication

- Severe thrombocytopenia (platelet count < 50,000/uL). Patients may restart study medication once the severe thrombocytopenia resolves and if considered appropriate by the investigator.
- Surgery or procedures associated with major haemorrhage, see Section 5.6.10
- Major bleeding, see Section 6.4.5.2
- Need of treatment with prohibited concomitant medications, see Section 5.6
- Stroke, see Section 5.6.1

For other surgery or other invasive procedures, study medication may be continued or interrupted temporarily at the discretion of the investigator, see Section 5.6.10.

5.8.2 Permanent discontinuation from study medication

- Patient decision: The patient is at any time free to discontinue treatment, without prejudice to further treatment.
- Investigator's decision:
 - 1 Incorrectly enrolled patient in whom the inclusion/exclusion criteria violation would put the patient at undue risk
 - 2 Adverse Event for which the Investigator thinks continued treatment may put the patient at undue risk
 - 3 Severe non-compliance to study protocol
 - 4 Pregnancy

Discontinuation of study medication does not mean discontinuation of follow-up or termination of study participation. Each permanent discontinuation should be communicated to the study team. For decisions around permanent discontinuation the EUCLID Study Physician can be consulted through the clinical hotline. Study assessments or telephone follow-up should be continued in all cases if possible, see Sections 5.8.3 and 5.9.

5.8.3 **Procedures for discontinuation of a patient from study medication**

Patients permanently discontinuing study medication should be given conventional therapy, if applicable, and should always be asked to continue the regular visits as described below.

A patient that decides to discontinue study medication will always be asked about the reason(s) for their desire to discontinue study medication and the presence of (if any) adverse events. These data will be ascertained and documented by the Investigator and recorded in the eCRF as appropriate. Adverse events will be followed up (see Sections 6.4.3 and 6.4.4); and the patient should return all study medications.

It is essential to collect as much data as possible for all patients throughout the study and especially all potential endpoint events. Complete withdrawal from the study (withdrawal of consent) has a direct impact on the potential validity of all study data and should be avoided wherever possible.

If the patient permanently discontinues study medication prior to the closure of the study, there could be several different options for their continuation in the study as described below.

5.8.3.1 The patient agrees to undergo the premature treatment discontinuation visit and then continue in-person study visits

The patient agrees to undergo the Premature Treatment Discontinuation Visit (PTDV) and then continue in-person study visits according to plan. This is the preferred option and patients who discontinue study medication will always be asked if they agree to this approach. If agreed, as above, the patient will undergo their PTDV at the time study medication is stopped. The patient will continue attending subsequent study visits according to schedule (Table 1) until the end of study date (ie, PACD) is declared, ie, when the pre-specified number of primary events has been reached. The patient will then return for their Study Closure Visit (SCV) as soon as possible but not later than 60 days after the Primary Analysis Censoring Date (PACD) has been declared. It is essential that whenever possible all patients attend the SCV in person.

5.8.3.2 The patient unwilling to continue in-person study visits but agrees to undergo modified follow-up

If the patient agrees, the PTDV visit should be done. The subsequent visits until the end of study date will be done as modified follow-ups (eg, regular telephone contacts, a contact at study closure, or other means) as specified in Section 5.8.3 in order to ascertain whether any endpoints or safety events had occurred. Such a patient has not withdrawn his/her consent or withdrawn from the study.

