Approximately 13,500 patients at approximately 950 study centres will be randomised (1:1) to receive either ticagrelor or clopidogrel monotherapy. The sample size is based on anticipated event rates that are related to the clinical stage of the disease. In an effort to achieve an appropriate claudication to critical limb ischaemia (CLI) final distribution ratio, the Executive Committee will monitor the Fontaine class (clinical stage) (Norgren (TASC II) 2007) and primary event rates and may cap enrolment to a particular subgroup based on the overall distribution and event rates. The Executive Committee will also monitor the proportion of patients enrolled with a prior history of MI and may cap enrolment on this subgroup as well.

Protocol Visits

Patients will return approximately every 6 months as outlined in Figure 1 and Table 1, for assessment of events related to the objectives of the study including efficacy, tolerability and safety. Assessment of treatment compliance and provision of study medication will be done at these visits. When visits are performed every 6 months, phone contacts will additionally be performed at a 3-month interval in between regular visits. The Investigator/study centre personnel will record non-serious AEs of interest (if any), DAEs, SAEs (if any), suspected clinical events (if any), study medication status, and use of concomitant medication. An unscheduled visit may be conducted as a result of the phone contact (eg, to follow-up on suspected clinical events).

Unscheduled visits

Unscheduled visits or phone contacts may be performed for event follow-up or early discontinuation of study medication.

Premature Treatment Discontinuation Visit (PTDV)

Patients who prematurely and/or permanently discontinued treatment with study medication but agreed to continue protocol visits should return for a PTDV, which will be done as soon as possible but no later than 15 days after prematurely discontinuing treatment with study medication. The PTDV will assess the same factors as the ESTV, with the only difference that patients who discontinue treatment early will be eligible for a PTDV.

End of Study Treatment Visit (ESTV)

When the predetermined number of primary events is anticipated, the following will occur:

- The Primary Analysis Censoring Date (PACD) will be declared by the Executive Committee
- All centre Investigators will receive communication to complete study visits as follows:

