 - All randomised patients should return for their ESTV as soon as possible but not later than 60 days after the Primary Analysis Censoring Date (PACD).

Study patients will be instructed to transition from study medication to accepted antiplatelet therapy per current practice guidelines and standards.

Study Closure Visit (SCV)

- All randomised patients should return for their SCV, 35 days \pm 5 days, after their ESTV.
- All patients who prematurely and/or permanently discontinued treatment with study medication should return for the SCV as soon as possible but not later than 60 days after the PACD.
- Patients who are not attending scheduled visits when PACD is declared will be contacted to schedule their SCV as soon as possible but not later than 60 days after PACD, for assessment of as many endpoints in the trial as possible (ie, health or vital status as per agreement at a minimum) in person, by telephone, by checking medical records or by collecting information from publicly available sources. It is strongly recommended that all patients attend their SCV in person.

For further details on procedures for discontinuing patients from study medication, refer to Section 5.8, and for the rare patient who must withdraw from study (study medication and visit assessments) refer to Section 5.9.

[figure not shown]

Figure 1 **Study Flow Chart**

dd = double dummy, db = double blind, PTDV = Premature Treatment Discontinuation Visit, PACD = Primary Analysis Censoring Date, ESTV = End of Study Treatment Visit, SCV = Study Closure Visit, od = once daily dosing, bd = twice daily dosing

- 1 Telephone follow-up will additionally be performed at a 3-month interval in between regular visits. Non-serious AEs of interest, DAEs, SAEs, suspected clinical events, study medication and concomitant medication status will be recorded. An unscheduled visit may be conducted as a result of the phone contact.
- 2 The Premature Treatment Discontinuation Visit (PTDV) is only done for patients who prematurely and/or permanently stop study medication.
- 3 The primary analysis censoring date (PACD) is time point in which the Executive Committee determines the number of events has been reached and study closure activities may begin.
- 4 The end of study treatment visit (ESTV) should occur as soon as possible but not later than 60 days after PACD.
- 5 The study closure visit (SCV) should occur within 35 days \pm 5 days from the last dose of study medication following PACD.

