a The study is event driven and the number of visits will depend on when the pre-estimated number of primary events has been reached. If study continues > 36 months, visits will continue every six months. Telephone follow-up will additionally be performed at a 3-month interval in between regular visits.

b The Premature Treatment Discontinuation visit (PTDV) is only done for patients who prematurely and/or permanently stop study medication.

c The End of Study Treatment Visit (ESTV) should occur as soon as possible but not later than 60 days after the Primary Analysis Censoring date (PACD).

d All randomised patients should return for their SCV, 35 days ± 5 days, after their ESTV; All patients who prematurely and/or permanently discontinued treatment with study medication should return for the SCV as soon as possible but not later than 60 days after the PACD. Patients who are not attending scheduled visits when PACD is declared will be contacted to schedule their SCV as soon as possible but not later than 60 days after the PACD, for

assessment of health status or vital status as per agreement, ie, in person, by telephone, by checking medical records or by collecting information from publicly available sources. It is strongly recommended that all patients attend their SCV in person.

- e Two ABI/TBI measurements must be taken (Visit 1 and Visit 2) to determine eligibility for the study for patients enrolling under ABI criteria. One ABI/TBI measurement must be taken at Visit 1 for those entering under the revascularization criteria. For all patients, ABI is then measured at Visit 4 and ESTV. The ABI measurement at Visit 1 must be ≤ 0.80 and the ABI measurement at Visit 2 must be ≤ 0.85 . If ABI is ≥ 1.40 at Visit 1 then TBI must be taken at Visit 2 for eligibility. The TBI measurement at Visit 1 must be ≤ 0.60 and the TBI measurement at Visit 2 must be ≤ 0.65 . The measurement and limb used at V1 and V2 should be the one that is used for all subsequent visits. Subsequent measurements will occur at the 6-month visit and PTDV/ESTV. The V1 and V2 ABI/TBI measurement for the first three subjects at each site will be assessed for quality.
- f Photoplethysmographic (PPG) signal is acceptable method of assessment of TBI.
- g Only in women of child-bearing potential.
- h EQ-5D and PAQ will be collected at V2 then annually starting at the 12 month visit, and PTDV/ESTVs.

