12.2.4 Censoring

The Executive Committee will monitor the accrual of the number of primary events and when appropriate predict and define a primary analysis censoring date at which time the pre-defined target number of events for the primary composite endpoint are expected to have occurred.

The primary analysis censoring date will be the common date at which all patients who are event free for the given endpoint and have not withdrawn consent for participating in the study will be censored in efficacy time-to-event analyses. Events that occur after the primary analysis censoring date but before the ESTV will also be collected and adjudicated. These events may be included in sensitivity analyses but not in the primary analysis.

Patients who have not had the event(s) in question will be censored at the earlier of (1) the primary analysis censoring date and (2) the last study contact when all components of the endpoint in question were assessed. In the analysis of CV death and composites including CV death censoring will occur at the earliest of (1), (2) and the date of death from non-cardiovascular causes. For endpoints not including death, all deaths are censoring events.

Complete endpoint information will be pursued with every effort for all patients regardless of their study medication status, unless they exercise their right to withdraw consent. Patients who have a non-fatal event will continue study follow-up. For patients who withdraw consent and for whom only vital status (known to be alive at study closure, or date of death) may be obtained from public records, the occurrence of all components of the primary endpoint cannot be assessed. Thus the primary endpoint and its components ischaemic stroke, MI, and CV death will be censored at the time of consent withdrawal for those patients who withdraw consent and for whom only vital status is known from public records. However, the determination of all-cause mortality as a sole outcome event will utilise all publicly known mortality data, even that extending beyond date of consent withdrawal. The vital status information will be included in the analysis of all-cause mortality as a single secondary endpoint, in sensitivity analyses and tabulations.

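### The primary analysis censoring date has two meanings, and for patients off study drug the closure visit can fall before it, so their lost follow-up would be tied to stopping treatment

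*Protocol*

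**What the plan says.** **When the PACD arises.** Section 3.1 (End of Study Treatment Visit) opens the closure steps with "When the predetermined number of primary events is anticipated, the following will occur". The first step is declaration of the PACD, and sites are then told to complete visits. Section 12.2.4 has the Executive Committee "when appropriate predict and define a primary analysis censoring date at which time the pre-defined target number of events" are expected to have occurred. In both places the date is set ahead of time. Figure 1 footnote 3 says instead that the PACD "is time point in which the Executive Committee determines the number of events has been reached and study closure activities may begin". Section 5.8.3.1 likewise equates declaration with the target having been reached.

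**Closure visit of patients off study drug.** Section 5.8.3.1 keeps them on regular visits until the PACD is declared, then asks for the SCV "as soon as possible but not later than 60 days after the Primary Analysis Censoring Date (PACD) has been declared". Section 3.1 says that the same patients "should return for the SCV as soon as possible but not later than 60 days after the PACD", and Table 1 footnote d agrees with it. For those no longer attending, Section 3.1 says: "Patients who are not attending scheduled visits when PACD is declared will be contacted to schedule their SCV as soon as possible".

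**Patients on study drug.** They have an end of study treatment visit (ESTV) no later than 60 days after the PACD, and an SCV 35 ± 5 days after that.

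**Censoring.** Section 12.2.4 censors event-free patients at the earlier of the PACD and "the last study contact when all components of the endpoint in question were assessed".

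**The concern.** The primary analysis is meant to follow every randomised patient to one common date, whether or not study drug was stopped. On the prospective meaning of the PACD, declaration comes first and the PACD later. A site that acts promptly on Section 5.8.3.1 could then see an off-drug patient for the last time between the two. That patient has no later protocol contact, so a primary event between the SCV and the PACD might not be ascertained, and the patient is censored at the SCV.

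The patients exposed are those who stopped treatment. If stopping differs between arms in frequency or in kind, the truncation differs too. Some events towards the target of 1364 could also be missed.

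**Working it through.** **1. The plan's own figure.** Inputs: HR 0.85, two-sided alpha 0.0494, 85% power (Section 12.3), 1:1 allocation (Section 3.1).

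- Schoenfeld events = 4 × (z for alpha + z for power)² / (ln HR)² = 4 × (1.965 + 1.036)² / (0.1625)² ≈ 1365, against 1364 stated.
- Power with 1364 events = Φ(√1364 / 2 × 0.1625 − 1.965) = 0.850.

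The target reproduces and is not in dispute. It serves only to scale a possible loss.

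**2. What each clock allows.** Let L be the days from declaration to the PACD. The protocol gives no value.

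- Section 5.8.3.1: the SCV falls 0 to 60 days after declaration, that is, from L days before the PACD to 60 − L days after it.
- Section 3.1 and Table 1 footnote d: the latest SCV is 60 days after the PACD, with no stated earliest day relative to it.

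| L (days) | SCV before the PACD under 5.8.3.1 | SCV before the PACD under 3.1 / Table 1 |
|---|---|---|
| 0 | no | no |
| above 0, up to 60 | possible, not forced | possible, not forced |
| 90 | forced, 30 to 90 days early | possible, not forced |
| 120 | forced, 60 to 120 days early | possible, not forced |

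The difference in anchor forces an early visit only when L exceeds 60 days. For a shorter lead, the cause is that the PACD is not stated as the lower limit.

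**3. Size, on assumed inputs.** Taken from the protocol: 13,500 patients and an aggregate event rate of about 4.1%, read as per year (Section 12.3). Assumed: 20-30% of patients off drug, and a gap of 1-3 months between last contact and PACD.

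- Low end: 13,500 × 0.20 = 2,700 patients; 2,700 × 1/12 = 225 patient-years; × 0.041 = 9.2 events; 9.2 / 1364 = 0.7%. Power with about 1355 events: 0.8475.
- High end: 13,500 × 0.30 = 4,050 patients; 4,050 × 3/12 = 1,012.5 patient-years; × 0.041 = 41.5 events; 41.5 / 1364 = 3.0%. Power with about 1322 events: 0.839.

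A wider range of assumptions, 10% off drug with a 15-day gap to 40% with a 120-day gap, gives about 2 to 73 events and power of 84.9% to 83.0%.

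For any given share and gap these counts lean high. They apply the gap to every off-drug patient, including those on modified follow-up and those already censored at consent withdrawal. They remove no deaths and no patients with an earlier primary event.

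**The case against.** The strongest reply is that Section 5.8.3.1, read alone, loses nothing. It equates declaration with the target having been reached, so visits run to that point and the SCV follows. Figure 1 footnote 3 likewise lets closure activities start only at the PACD. If declaration and PACD coincide, the two clocks agree. That is right as far as it goes. But Section 12.2.4 governs the primary analysis, and its PACD is predicted; Section 3.1 declares it when the target is anticipated. The passages cannot all stand.

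A reader might infer three stronger things, none of which the document supports:

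- *That closure has no earliest date at all.* Section 5.8.3.1 has the patient return after declaration, and Figure 1 footnote 3 implies a start at the PACD. What is missing is an explicit rule that the off-drug contact falls on or after the predicted date of Section 12.2.4.
- *That on-drug patients lose follow-up in the same way.* Figure 1 footnote 5 times their SCV from the last dose following the PACD, and Section 12.2.4 provides for events between the PACD and the ESTV. Even an ESTV 30 days early would be followed by an SCV 30 to 40 days later, 0 to 10 days after the PACD.
- *That bias between arms is shown.* It is only possible; the protocol gives no discontinuation figures by arm.

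There are also safeguards. Section 5.5.2 promises a study closure plan. Section 12.2.4 pursues complete endpoint data regardless of medication status. The target of 1364 is a minimum, and the Executive Committee sets the PACD while watching event accrual. Patients on modified follow-up (Section 5.8.3.2) are contacted until the end of study date. The sensitivity analysis in Section 12.2.1 addresses exactly the time from censoring to the PACD. These limit the harm. However, that analysis allocates hypothetical events and cannot recover real ones that a single later contact would have found.

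**Conclusion.** The contradiction is real and should be corrected. The PACD is a predicted date in two places and an attained one in two others. The off-drug closure visit is counted from declaration in one section and from the PACD in others. No passage expressly places that visit on or after the PACD.

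Loss of follow-up is conditional: it needs a PACD declared ahead of time, as Sections 3.1 and 12.2.4 provide, and either a promptly held SCV or a lead above 60 days under Section 5.8.3.1. On the assumed shares and gaps, about 9 to 42 events are at risk and power falls by roughly 0.2 to 1.1 points. That is small. The point matters because the censoring would follow treatment discontinuation, in an analysis that relies on follow-up to a common date irrespective of treatment.

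**What to change.** - Make the prospectively set calendar date of Section 12.2.4 the only definition of the PACD, and bring Figure 1 footnote 3 and Section 5.8.3.1 into line with it.
- Align Section 5.8.3.1 and Table 1 footnotes c and d so that every closure window is counted from the PACD.
- Continue scheduled visits and calls until the PACD, not until its declaration.
- Require endpoint status to be ascertained through the PACD for every patient who has not withdrawn consent, with one further telephone or records contact for anyone last seen before it.

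The cost is wording in a few places and at most one extra contact per affected patient. The event target, the analysis method and the treatment rules do not change.
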